12 STATISTICAL CONSIDERATIONS

12.1 General Design Issues

This study will address the primary objective using a cluster randomized stepped wedge design. Surgical practices, or clusters, will be randomized in 5 tranches to receive the NOHARM intervention; outcomes of patients treated by these teams will be compared by intervention status of the team. The primary statistical hypothesis is that pain and function measures will be lower and higher, respectively, in the patients treated under the intervention conditions, when compared with non-intervention patients in those same practices.

The cluster randomized stepped-wedge design will allow us to stagger the NOHARM implementation while increasing statistical power. The alternative to staggering the implementation would be to implement at all sites at the same time, which is impractical from a resource perspective. The stepped-wedge design allows each site to serve as its own control, reducing the bias due to imbalanced risk factors across clusters. Contamination does pose some threat to the internal validity of stepped wedge designs when, as here, the intervention rolls out sequentially in adjacent clusters. The 22 NOHARM clusters will minimize potential contamination by capitalizing on geographical separations in the built environments used to deliver perioperative care including different buildings in some cases, as well as subspecialty-designated inpatient wards, office suites, etc.

The primary hypothesis is that the NOHARM intervention will reduce patient reported pain and increase patient reported function following designated surgical procedures relative to patients treated under usual care. The primary outcome – a composite of patient reported pain and function – 3 months post-operatively will be assessed using validated patient reported outcomes.

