12.2.1 Treatment Assignment Procedures

In order to balance cluster characteristics, we applied a constrained randomization procedure. Constrained randomization allows us to balance a larger number of cluster characteristics than is possible through

stratification. Here the key cluster characteristics to be balanced were: site (6 locations), volume (estimated using 2018 data), procedures (3 groups), and number of teams (1-4). Given only 22 sites, it would not be practical to stratify or apply minimization, while constrained randomization allows us to select an allocation of sites to waves from among a set of allocations that has better balance on these factors.

Specifically, we generated 100,000 allocations of the 22 clusters to 5 waves. For each allocation, we then calculated a balance metric B as follows. For each characteristic c listed above, let $X(c)_i$ be the value of c for each cluster $i=1,\dots,22$. For categorical factors X is an indicator, for volume and number of teams X is a number, rescaled to range from 0-1. Let $w=0,\dots,5$ be the baseline ($w=0$) and 5 intervention waves; and for a given allocation, let S_i = the first wave at which cluster i is allocated to intervention. Then we calculate for each allocation the balance metric

$$B = \sum_{w=0,5} (\bar{S}_i - w) \left| \sum_c X(c)_i (S_i \leq w) - \sum_c X(c)_i (S_i > w) \right|$$

After generating 100,000 allocations, we constrained selection to those with values of B in the lowest decile; we then selected one allocation randomly from those 10,000 ‘acceptable’ allocations. This process resulted in a full allocation of all 22 sites to waves 1-5 prior to initial intervention.

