12.5 Data Analyses

Because patients are randomized in clusters, all statistical methods will account for potential correlation of measures within clusters. Such methods include cluster adjusted standard errors for t-tests and χ^2 -tests, and mixed effects models. Patient characteristics will be summarized by intervention status, and tested for difference between intervention groups; any factors which are imbalanced will be accounted for in the main analyses. Factors assessed for balance and potential inclusion in pre-specified analyses are those listed in Section 13.1.1 and all baseline measures listed in 13.1.2.

The primary and secondary outcomes will be compared between intervention groups using mixed effects generalized linear models. Each model will include an indicator for intervention group; a random intercept for cluster; cluster level factors that were used to constrain randomization; calendar time; surgery type; and any patient factors that were imbalanced across groups.

The model details for each outcome are as follows:

1. PROMIS CATs (anxiety (1°), physical function (1°), pain (1°)). These are continuous measures, collected at two time points, pre-operative and 3 months post-operative. To assess the impact of the intervention on these we will estimate three separate models. If Y_{ijt} is the measure at time $t=1,2$ of the i th patient treated by the j th cluster, then we will estimate

$$Y_{ij2} = \beta_0 + \beta_I I_{ij} + \beta_B Y_{ijo} + \beta_T T + \mathbf{B}_X \mathbf{X}_{ij} + \mathbf{B}_Z \mathbf{Z}_j + u_j + e_{ij} \quad (1)$$

where I_{ij} indicates the intervention status, T is calendar time, $u_j \sim N(0, \tau^2)$ is a cluster level random effect, X_{ij} is a vector of patient characteristics, including surgery type, Z_j is a vector of cluster characteristics used for randomization, and e_{ij} is a residual error. By testing $\beta_I = 0$ we can assess whether the intervention is associated with changes in the corresponding measure.

2. NPPC use. This is collected as a binary value for each of 14 modalities, collected at one time point, 3 months post-operative. We will sum these to create a score, and use a model similar to (1) but without a baseline value Y_{ij0} :

$$Y_{ij} = \beta_0 + \beta_I I_{ij} + \beta_T T + \mathbf{B}_X \mathbf{X}_{ij} + \mathbf{B}_Z \mathbf{Z}_j + u_j + e_{ij} \quad (2)$$

Again by testing $\beta_I = 0$ we can assess whether the intervention is associated with changes in the corresponding measure.

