13.3.4 Protocol Deviations

Protocol deviations will be reported promptly to the Mayo Clinic IRB upon the study team being made aware of the deviations. The main opportunity for protocol deviations is the mis-routing of patients to wrong study arm (intervention or control). Care will be taken to make sure the EHR assignment algorithms are functioning properly. Protocol modifications will be made as new tranches are brought into the intervention arm of the study.

The following are examples of potential protocol deviations which will be carefully avoided, but reported if they occur:

1. Implementing the intervention without practice approvals.

As indicated in the protocol and elsewhere, we will be engaging with practice leadership in advance of implementing the NOHARM intervention. Failure to duly engage practice leadership and obtain documented approval prior to implementing the intervention in specific surgical practices would violate expectations set in the protocol.

2. Incorrect routing of patients to intervention/control arms.

Patient assignment to either the treatment or control arm of the study within the EHR will be done via pre-specified algorithms. Rigorous testing and validation will be done to ensure the algorithms are functioning as expected. Should the algorithms fail to properly assign patients to the treatment or control arm of the study, appropriate action will be taken to refine the algorithms to prevent further mis-assignment and the affected patients will be accounted for, as appropriate, in the study analyses.

3. Failure to monitor trial for data quality and patient safety.

Per the protocol, we will monitor study implementation—particularly within the surgical practices in which the NOHARM intervention has been implemented—to ensure that the intervention is functioning as designed/intended and that critical data points are being captured. Further, the protocol assumes that data essential for monitoring patient safety and ensuring data quality will be abstracted as needed and made available to the data safety and monitoring board for review.

4. Study staff not included in IRB documentation.

All personnel on the study who will be involved with the conduct of the research must be included in IRB documentation per Mayo Clinic policy. This excludes members who are involved with NOHARM as Standard of

Care. Failure to disclose personnel actively involved in the study conduct will constitute a protocol deviation.

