14.2 Informed Consent Forms & Authorization Considerations

A waiver of informed consent is being requested for this study, which presents no more than minimal risk of harm to subjects. Because this is a population-based, EHR-embedded study, it is not practical to conduct the research without the waiver of consent. We do not feel the waiver of informed consent will adversely affect the rights or welfare of the subjects.

In lieu of consent, we have sought out and confirmed Mayo Clinic Practice leadership support for the trial. In the 3-6 months prior to each wave of trial implementation we will confirm each individual practices' willingness to participate in the trial. Because some practices will not be randomized until 2023, securing their endorsement now, did not make sense.

See Section 15 – Ethical Considerations for more information.

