Appendix A: Clinician Participants

Clinician Participants

The clinical practices of care teams involved in the care of surgery patients targeted by the NOHARM intervention—including surgeons, nurses, physical therapists, pain management specialists—will be impacted by the bundled NOHARM intervention. In the course of providing care to surgical patients in active intervention clusters, clinicians will be alerted to non-pharmacological pain management strategies (via CDS tools embedded in the EHR) for which patients have expressed preference. Within their routine workflows (i.e. interface with patients), clinicians will be prompted to engage patients about their preferred post-acute pain management strategies.

Because of this practice impact, clinicians will be considered “participants” in the NOHARM pragmatic trial (in the same way as they have been construed in the pilot application IRB# 20-001864). This determination has been affirmed by the Mayo Clinic IRB executive committee (January 2020 meeting).

Accrual

Based on data from 2018 on the 22 surgery types targeted by the NOHARM trial (minus neuro / spine surgery which is the focus of the NOHARM pilot trial – IRB# 20-001864) we estimate there to be approximately 225 surgeons in the enterprise who are routinely performing surgery. We will inflate this number to 300 to account for physicians performing one of the target surgery types less frequently. To this figure, we will add 0.5 residents / and 0.5 physician assistants per surgeon (+300). Assuming a median hospital stay of 3 days (9 nursing shift changes), we will add 9 nurses X 300 surgeons (+2700). Finally, assuming 0.5 physical therapist per surgeon and 0.2 integrative medicine specialist per surgeon, we will add 210 clinicians. This brings our total estimated clinician accrual to 3510 participants.

Consent and Data Collection

1. Given the ubiquity of the intervention and the volume of clinicians touched by the trial it will not be practicable to obtain individual consent for participation.
2. Clinician “consent” will be granted in the form of “whole practice consent” granted by individual surgical practice leadership within the institution as a pre-requisite for implementation in specific surgical practices.

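### The intervention indicator is not tied to the randomised wave, and no rule covers practices that defer or refuse after allocation

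*Combined protocol and SAP*

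**What the plan says.** **Comparison and model term.** Section 12.1 states that "outcomes of patients treated by these teams will be compared by intervention status of the team". In the primary model of 12.5 the exposure is described only as follows: "where I_{ij} indicates the intervention status, T is calendar time". Section 7.3 draws control data from patients under usual care in clusters that have not yet been switched on.

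**Allocation.** Section 12.2.1, on the constrained randomisation: "This process resulted in a full allocation of all 22 sites to waves 1-5 prior to initial intervention".

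**Confirmation and approval.** Section 14.2: "In the 3-6 months prior to each wave of trial implementation we will confirm each individual" practice's willingness to take part. Section 13.3.4 makes approval binding: "Failure to duly engage practice leadership and obtain documented approval prior to implementing the intervention in specific surgical practices would violate expectations". Appendix A describes consent by practice leadership "as a pre-requisite for implementation in specific surgical practices".

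**Departures.** The only analysis rule found is in 13.3.4, for patients whom the algorithm sends to the wrong arm: "the affected patients will be accounted for, as appropriate, in the study analyses". Nothing was found for a practice that defers or refuses, and there is no intention-to-treat statement.

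**A conflict on timing.** Section 14.2 also says: "Because some practices will not be randomized until 2023, securing their endorsement now, did not make sense". This does not fit 12.2.1, unless randomised there means activated.

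**The concern.** In a stepped wedge trial the randomised item is the date at which a cluster crosses over. If the indicator follows that date, its timing is independent of what is happening in the practice. If it follows actual activation, and practices can influence activation after allocation, that independence is lost for those that depart.

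The trial is meant to detect about 0.05 SD, so a bias of a few hundredths of an SD would matter. There is also a simpler problem. With the definition left open, the coding could be chosen once the departures are known.

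**Working it through.** **1. The text.** Allocation comes first (12.2.1), willingness is checked later (14.2), and activation needs approval (13.3.4, Appendix A). A practice that says not yet, or no, therefore cannot be switched on at its randomised time. Section 7.3 defines controls by activation, so such a practice's patients fall on the control side during the delay. Neither 12.1 nor 12.5 corrects this.

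**2. The plan's own figure.** Section 12.2 gives a detectable effect of 0.048-0.055 SD. It cannot be reproduced from its stated inputs, because alpha, power and cluster-period sizes are not given. With the Hussey-Hughes standard error, 5% two-sided alpha and (z_0.975 + z_power) x SE, 114,000 patients give 0.029-0.034 SD at 80% power. The stated range is approached with about 40,000 analysed at 80% power (0.049-0.056) or about 57,000 at 90% (0.048-0.055). It serves here only as a yardstick.

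**3. Simulation set-up.**
- From the plan: 22 clusters, five waves plus baseline, 114,000 patients, ICC 0.037.
- Derived: 114,000 / (22 x 6) = 864 per cluster-period; with residual variance 1, cluster variance = 0.037 / (1 - 0.037) = 0.0384.
- Assumed: equal cluster sizes, categorical period effects, random cluster intercept, no true effect, the number of deferring practices and why they defer.
- Outcome in cluster k, period t: period effect + cluster level u_k + shock g_kt + error.
- Indicator by randomised wave: 1 if t >= w_k. By actual activation: 1 if t >= w_k + d_k, with d_k = 1 for a one-wave deferral.

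**4. Bias in SD with no true effect** (pain scale).

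| Why practices defer | By actual activation | By randomised wave |
|---|---|---|
| At random, 2-6 practices | about 0 | about 0 |
| Persistently higher pain, 2-6 | at most about 0.001 in favour | below 0.001 |
| Poor scheduled period, shock SD 0.05; 2, 4, 6 | 0.013, 0.022, 0.027 in favour | 0.0005 or less |
| Same mechanism, outright refusal; 2, 4 | 0.007, 0.012 in favour | 0.001 or less |
| Poor scheduled period, independent shocks at 10-20% of cluster variance, 2-6 worst | 0.016-0.047 in favour | about 0.001 or less |
| Poor preceding period, independent shocks, otherwise the same | 0.002-0.011 **against** | about 0.001 or less |
| Poor preceding period, autocorrelated shocks | 0.002-0.012 in favour | about 0.001 or less |

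The third and fifth rows agree. The bias is proportional to the shock SD, which at 10% and 20% of 0.0384 is sqrt(0.00384) = 0.062 and sqrt(0.00768) = 0.088. Scaling the unrounded results for two and six practices gives 0.0125 x 0.062/0.05 = 0.016 and 0.0273 x 0.088/0.05 = 0.048.

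**5. Which period drives the decision.** March 2021 to August 2023 is 30 months, so five equally spaced waves (an assumption) are 30/5 = 6 months apart. A decision taken 3-6 months ahead falls largely in the preceding period. With independent shocks the sign then reverses: deferral shortens the practice's treated phase, so its poor control period carries less weight in the within-cluster contrast. With shocks that persist, the bias again favours the intervention but is small.

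**6. Cost of coding by randomised wave.** With a true effect of -0.050 SD and random one-wave deferral of 2, 4 and 6 practices, the estimates are about -0.046, -0.042 and -0.038 SD, or 8%, 15-16% and 23% dilution. Two or four outright refusals give about -0.046 and -0.041 SD.

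**The case against.** A reader might infer that the plan prescribes an as-treated analysis which would break the randomisation. The documents do not support that. Neither 12.1 nor 12.5 says that status means actual status. Several sections tie delivery to the schedule: section 6 links receipt of the intervention to whether the surgery date falls within the rollout, and 7.3, 8.3.2 and section 11 say activation follows the randomisation scheme or stepped-wedge schedule. If it does, the two codings are identical. On mis-routing, 12.1 speaks of the status of the team, so a mis-routed patient may well keep the team's status already.

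Nor is there evidence of departures. None is documented, 14.2 reports that institutional practice leadership already supports the trial, and nothing says that practices under strain would be the ones to defer. Because each cluster is its own control, a stable difference between deferring and other practices is absorbed by the cluster intercept.

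Most of this stands, and it limits the point to an unstated definition with a possible bias of uncertain sign. It does not close the gap. The schedule passages describe the intended rollout and do not say how a departure is analysed, while the approval requirement makes departures possible. The protocol itself anticipates mis-routing (13.3.4) and loss of a site (12.3).

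**Conclusion.** The point holds as a gap in the plan. The indicator is not tied to the randomised wave, no rule covers a practice that defers or refuses, and the literal wording of 7.3 and 12.1 would classify such a practice by activation. This could bias the primary comparison; it does not follow that it would.

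For 2-6 of 22 one-wave deferrals, the size runs from about 0.01 SD against the intervention to about 0.05 SD in its favour, compared with a stated detectable effect of 0.048-0.055 SD. The upper end requires that the worst-placed practices defer, that the scheduled period itself drives the decision, and that shocks are independent between periods. With the decision taken a period earlier, closer to the timing in 14.2, the bias is about 0.01 SD or less in either direction. The mechanism, the number of deferrals and the variance share are assumptions. Coding by randomised wave brought the bias to about 0.001 SD or less in every scenario.

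**What to change.** - In 12.1 and 12.5, define I_ij = 1 if the surgery date is on or after the activation date of the cluster's randomised wave, and 0 otherwise, whatever the actual activation or routing.
- State that deferring or refusing clusters stay in the primary analysis in their allocated wave. In 13.3.4, replace the open wording on mis-routed patients with the same rule.
- Report analysis by actual activation as a sensitivity analysis, with a table of scheduled and actual activation dates by cluster.
- Reconcile 14.2 with 12.2.1 on when practices are randomised. With equal spacing, the fifth wave would start about 24 months after March 2021, in March 2023, so 14.2 may mean activated; the sponsor should confirm.

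This takes a few sentences and uses an allocation that already exists. The price is the dilution shown above if practices depart, an error towards no effect. If activation follows the schedule, nothing changes.

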12.2 Sample Size and Randomization

Using pain data for 6,261 patients with these procedures at six sites, we estimated the intra-cluster correlation coefficient (ICC) for the pain score to be modest $\rho = 0.037$. To assess minimal detectable effects, we simulated a large number of randomizations and estimated the detectable effect for each. Specifically, for $P = 1, \dots, 5000$ permutations, the 22 clusters were randomly assigned to 5 waves. For each permutation, the closed form solution of Harrison et al (2019) was used to estimate $SE(Q)$ (derived from the formula of Hussey, Hughes (2008)) for true effect Q . We used the values $\sigma^2 = 1$ and $\tau^2 = 0.488$ for the within and between variance components so that detectable effects would be in SDs, and assumed ICC would be 0.037. Over the 5,000 permutations, the detectable effect ranged between 0.048SD and 0.055SD.

12.2.1 Treatment Assignment Procedures

In order to balance cluster characteristics, we applied a constrained randomization procedure. Constrained randomization allows us to balance a larger number of cluster characteristics than is possible through

stratification. Here the key cluster characteristics to be balanced were: site (6 locations), volume (estimated using 2018 data), procedures (3 groups), and number of teams (1-4). Given only 22 sites, it would not be practical to stratify or apply minimization, while constrained randomization allows us to select an allocation of sites to waves from among a set of allocations that has better balance on these factors.

Specifically, we generated 100,000 allocations of the 22 clusters to 5 waves. For each allocation, we then calculated a balance metric B as follows. For each characteristic c listed above, let $X(c)_i$ be the value of c for each cluster $i=1,\dots,22$. For categorical factors X is an indicator, for volume and number of teams X is a number, rescaled to range from 0-1. Let $w=0,\dots,5$ be the baseline ($w=0$) and 5 intervention waves; and for a given allocation, let S_i = the first wave at which cluster i is allocated to intervention. Then we calculate for each allocation the balance metric

$$B = \sum_{w=0,5} (\bar{S}_i - w) \left| \sum_c X(c)_i (S_i \leq w) - \sum_c X(c)_i (S_i > w) \right|$$

After generating 100,000 allocations, we constrained selection to those with values of B in the lowest decile; we then selected one allocation randomly from those 10,000 ‘acceptable’ allocations. This process resulted in a full allocation of all 22 sites to waves 1-5 prior to initial intervention.

12.3 Interim analyses and Stopping Rules

This is a minimal risk study for which there is no planned interim analysis. Interim analysis may be conducted at the request of the DSMB or if necessitated by unforeseen changes in the study plan (e.g. loss of a study site). Similarly, there are no pre-specified stopping rules as the probability and magnitude of adverse experiences are not greater than those ordinarily encountered in daily life.

12.4 Outcomes

Outcomes will be collected via the Epic EHR. PROMs will be collected using interfaces available to patients in their MyChart patient portals or the Welcome tablet functionality at point of care as available. Because outcomes will be either PROMs or data entered by providers during routine care delivery, requirements for adjudication will be minimal. Health care utilization is an exception in that criteria for hospitalizations vary based on designations of observational status. The NOHARM Data Management working group will identify hospitalizations that may require adjudication, including ER stays that exceed 24 hours. A committee blinded to a patient’s affiliation with an activated or control cluster will determine whether to designate such instances as hospitalizations.

The cadence and mode of PROM data collection are outlined below. PROMs comprise the NOHARM trial’s co-primary and a majority of its secondary outcomes. PROMs will additionally be collected for use in describing the study population and for analytic adjustments.

